9.4.2 Analysis of LTE Treatment Period and OLE Treatment Period

All the exploratory endpoints collected during the LTE Treatment Period and the OLE Treatment Period will be summarized with appropriate summary statistics over time, using the same definitions given above.

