8. ANALYSIS SETS

The following analysis sets for the Induction Treatment Period are defined as follows:

Full Analysis Set (FAS): The FAS consists of all randomized participants receiving at least 1 dose of study treatment. Under this approach, participants are counted in the treatment group to which they were randomized, regardless of the treatment received during the study.

Modified Full Analysis Set (mFAS): For a given endpoint (see [Section 23](#), Appendix II), mFAS consists of all randomized participants who received at least 1 dose of study treatment and contribute at least one complete endpoint assessment for at least one post-baseline Induction visit. Participants will be analyzed according to the treatment to which they were randomized.

Per Protocol (PP) Set: The PP Set consists of all participants in the primary endpoint mFAS who received $\geq 80\%$ and $\leq 120\%$ of study treatment and do not have a protocol deviation preventing contribution to the primary analysis of the primary efficacy endpoint. Participants experiencing an intercurrent event during the Induction Treatment Period and not experiencing other deviations preventing contribution to the primary and key secondary analyses of the primary and key secondary efficacy endpoints will be included in the PP set and treated as non-responders in these analyses ([Section 3.5](#)).

Safety Set: The Safety Set consists of all randomized participants who received at least 1 dose of study treatment. For this population, participants are analyzed according to the treatment received, regardless of randomization. The Safety Set will be used for all safety analyses in the Induction Treatment Period.

The following analysis sets for the LTE and OLE Treatment Periods are subsets of the analysis sets of the Induction Treatment Period, as defined below:

FAS-Extension Treatment (FAS-ET) Set: The FAS-ET Set consists of all randomized participants who received at least 1 dose of study treatment in the LTE or the OLE Treatment Period. Under this approach, the original treatment groups as assigned at randomization will be used throughout LTE. In general, participants will be analyzed according to protocol-specified intended study treatment dose in FAS-ET analyses. Additional details are provided for specific analyses described elsewhere in this SAP.

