16.1.2 Missing Data Methods for the Primary Efficacy Variable

The concept of non-response for participants with non-missing Week 13 Induction primary efficacy outcomes is described at the beginning of [Section 16](#). For participants with missing Week 13 Induction Treatment Period primary efficacy outcomes, the following missing data methods will be used:

- Primary method: single imputation as non-responder
- Sensitivity analyses
 - multiple imputation under missing at random (MAR)
 - multiple imputation with Copy Reference (CR) under missing not at random (MNAR)
 - tipping point analysis
- Supplementary analyses: mFAS and PP set analysis with data as observed

These methods are discussed in more detail below. See [Section 29](#) (Appendix VIII) for a tabular presentation of the relationship between intercurrent events, missing data, and response imputation.

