16.4 Exploratory Efficacy

The endpoints described here will be analyzed separately, as appropriate, for the Induction Treatment Period, Long-Term Extension Treatment Period (LTE), and Open-Label Extension (OLE). In general, when an endpoint refers to Induction Study Period visits, that endpoint will be included in the Induction Period Analysis, but restricted to visits associated with the Induction Study Period. For example, CRP change from baseline analysis will be included in the Induction Period Analysis, but restricted to Weeks 1, 4, 8, and 13. LTE and OLE analyses for the same endpoint may differ not only with respect to the participant set but also with respect to statistical methodology.

- Proportion of participants with histologic remission at Week 13 using RHI
- Proportion of participants with histologic remission at Week 13 using NHI
- Proportion of participants with histologic improvement at Week 13 using RHI
- Proportion of participants with histologic improvement at Week 13 using NHI
- Proportion of participants with clinical remission after 52 weeks of treatment
- Proportion of participants with clinical remission after 13 and 52 weeks of treatment
- Proportion of participants with symptomatic remission at Weeks 18, 26, 36, and 52
- Proportion of participants with endoscopic remission with histologic remission after 52 weeks of treatment
- Proportion of participants with endoscopic improvement-histologic remission after 52 weeks of treatment
- Proportion of participants with endoscopic and clinical remission after 52 weeks of treatment

- Proportion of participants with endoscopic remission, histologic remission, and clinical remission after 52 weeks of treatment
- Proportion of participants with HEMI after 52 weeks of treatment
- Proportion of participants with clinical response after 52 weeks of treatment
- Proportion of participants with symptomatic response at Weeks 18, 26, 36, and 52
- Proportion of participants with symptomatic response at OLE Week 13, and at each additional OLE visit
- Proportion of participants with any decrease from baseline in Geboes Index score at Week 52
- Change from baseline in FCP at Weeks 1, 4, 8, 13, 26, 36, 52, and at visits during the OLE
- Change from baseline in CRP at Weeks 1, 4, 8, 13, 26, 36, 52, and at visits during the OLE
- Change from baseline in PMS at Weeks 4, 8, 13, 18, 26, 36, 52, and at visits during the OLE
- Change from baseline in total MCS at Week 52

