- Change from baseline in IBDQ score at Weeks 13 and 52
- Change and percentage change from baseline in lymphocyte counts at Weeks 1, 4, 8, 13, 26, 36, and 52
- Change and percentage change from baseline in Rectal Bleeding at Weeks 1, 4, 8, 10, 13, 18, 26, 36, and 52
- Change and percentage change from baseline in Stool Frequency at Weeks 1, 4, 8, 10, 13, 18, 26, 36, and 52

The first fifteen exploratory endpoints will be handled as responder analyses and analyzed similarly to the primary endpoint, per timepoint, using the CMH test with the same as-randomized stratification factors. The FAS set will be used for this purpose and treatment group comparisons (VTX002 60 mg vs placebo; VTX002 30 mg vs placebo) will be as-randomized. No adjustment for multiplicity will be made and the nominal Type 1 error rate for each hypothesis test is $\alpha=0.05$.

The last eight exploratory endpoints are quantitative. [Table 7](#) describes the analyses and analysis sets to be used for treatment group comparisons for these endpoints.

For the parameters listed in [Table 7](#), when Summary Statistics are indicated absolute values, change from baseline, and percent change from baseline will be summarized. The analysis set in the table denotes how treatment group is handled in these summaries. Additionally, figures for mean (SD) absolute value - time curve during study will be created for the following parameters:

CRP, lymphocyte counts, and neutrophil counts using normalized pooled data from both central laboratories. Separate figures will be generated for induction, LTE and OLE Treatment Periods.

Table 7. Quantitative Exploratory Endpoints and Analysis Sets

Parameter	Timepoint	Comparison	Methodology	Analysis Set
FCP (central laboratory)	Induction treatment: Weeks 1, 4, 8, 13	VTX002 60 mg vs Placebo	MMRM ^a , Summary Statistics ^b	FAS
		VTX002 30 mg vs Placebo		FAS
	LTE/OLE: Weeks 26, 36, 52 and each visit during the OLE	VTX002 60 mg vs Placebo		FAS
		VTX002 30 mg vs Placebo		FAS
CRP (central laboratory)	Induction treatment: Weeks 1, 4, 8, 13	VTX002 60 mg vs Placebo		FAS
		VTX002 30 mg vs Placebo		FAS
	LTE/OLE: Weeks 26, 36, 52 and each visit during the OLE	VTX002 60 mg vs Placebo		FAS
		VTX002 30 mg vs Placebo		FAS
PMS	Induction treatment: Weeks 4, 8, 13	VTX002 60 mg vs Placebo	FAS, PP	
		VTX002 30 mg vs Placebo	FAS-ET	
	LTE/OLE: Weeks 18, 26, 36, 52 and each visit during the OLE	VTX002 60 mg vs Placebo	FAS-ET	
		VTX002 30 mg vs Placebo	FAS-ET	

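### SAP 16.4 sends symptomatic response at OLE visits to a CMH test against placebo in the FAS, although everyone in the OLE takes open-label 60 mg; the endpoint should be described, not tested

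*SAP*

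**What the plan says.** SAP 16.4 lists 24 exploratory endpoints. The fifteenth is "Proportion of participants with symptomatic response at OLE Week 13, and at each additional OLE visit". The rule after the list is "The first fifteen exploratory endpoints will be handled as responder analyses and analyzed similarly to the primary endpoint, per timepoint", by CMH test with the as-randomized strata. The sentence fixing the set and contrasts begins "The FAS set will be used for this purpose and treatment group comparisons (VTX002 60 mg vs placebo; VTX002 30 mg vs placebo", and both contrasts are as randomized. On error control: "No adjustment for multiplicity will be made and the nominal Type 1 error rate for each hypothesis test is" 0.05.

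The FAS does not depend on entering the OLE. SAP 8 says "The FAS consists of all randomized participants receiving at least 1 dose of study treatment". For a missing primary outcome, SAP 16.1.2 gives "Primary method: single imputation as non-responder". SAP 3.5 extends the primary estimand's population and intercurrent-event handling, in general terms, to exploratory endpoints.

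All OLE entrants are titrated to open-label 60 mg (SAP 4.3.3, Protocol 6.3.1). Week 13 clinical responders continue in the blinded LTE on their assigned treatment, and non-responders may enter the OLE (Protocol 4.1.3 and 4.1.4).

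Protocol 9.4.2 states that exploratory endpoints collected in the LTE and OLE "will be summarized with appropriate summary statistics over time". SAP 18 declares two departures from the protocol, on Screening day numbering and on separate FCP models, and neither concerns this test.

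In SAP Table 7, the FCP and CRP timepoint "LTE/OLE: Weeks 26, 36, 52 and each visit during the OLE" stands beside dose-versus-placebo comparisons in the FAS. The PMS rows also include OLE visits, but in the FAS-ET.

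**The concern.** At an OLE visit no one is on placebo. A CMH test of 60 mg against placebo there compares past randomized arms after everyone has moved to the same drug and dose. The participants who supply OLE data are also selected by their Week 13 outcome, which the randomized treatment is expected to influence.

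The choice of denominator then matters. If every dosed participant is kept and those with no OLE visit are scored as non-responders, the arm with more Week 13 responders sends fewer people straight into the OLE and may show a lower OLE response for that reason alone. At stake is a nominal p-value that cannot be read as a treatment effect and might point the wrong way, in a part of the study for which the protocol plans only summaries.

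**Working it through.** **1. Does the rule capture this endpoint?** Counting the list in SAP 16.4: items 1 to 14 are histologic, Week 52 and LTE responder endpoints; item 15 is symptomatic response at OLE visits; item 16 is any Geboes decrease at Week 52; items 17 to 24 are the eight quantitative endpoints. Item 15 is inside the CMH rule. Item 16 falls under neither rule, so the count may be a slip, but raising it to sixteen would still include item 15.

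**2. Is there another rule for it?** SAP 16.4 says that the OLE participant set and methodology may differ, but gives no alternative for this endpoint. The symptomatic-response row of Table 7 covers Week 13 and Weeks 18 to 52, with summary statistics only, and does not list OLE visits.

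**3. Size of the possible artefact.** The plan gives no figure to reproduce here. Let R be Week 13 clinical response in an arm, u the share of Week 13 non-responders who enter the OLE and reach the visit, s the same share for LTE participants, and r the OLE symptomatic response among those seen. Set r, u and s equal across arms, with r the same for both routes of entry, so that there is no true difference in the OLE. If all other FAS members count as non-responders:

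FAS proportion = [(1 - R) × u + R × s] × r

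Difference (60 mg minus placebo) = -(R60 - Rplacebo) × (u - s) × r

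All rates are assumed: R = 0.60 and 0.35, r = 0.50, u = 1.

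| s | 60 mg | Placebo | Difference (points) |
|---|---|---|---|
| 0 | 0.40 × 0.50 = 20.0% | 0.65 × 0.50 = 32.5% | -12.5 |
| 0.5 | (0.40 + 0.30) × 0.50 = 35.0% | (0.65 + 0.175) × 0.50 = 41.25% | -6.25 |
| 0.8 | (0.40 + 0.48) × 0.50 = 44.0% | (0.65 + 0.28) × 0.50 = 46.5% | -2.5 |
| 1 | 50.0% | 50.0% | 0 |

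At s = 0, moving r from 0.40 to 0.60 changes the gap from -10 to -15 points. The share s matters more.

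**4. Wider range.** Take u = 0.90, Week 13 response pairs of 50/30%, 60/35% and 65/40%, and r of 0.40 to 0.60. The gap is -7.2 to -13.5 points at s = 0, -3.2 to -6.0 at s = 0.5, -0.8 to -1.5 at s = 0.8, and 0 at s = 0.9, where both routes have equal uptake. With 63 per arm (SAP 6), an unstratified two-proportion approximation gives a 16% to 41% chance of nominal p < 0.05 against 60 mg at s = 0, and 6% to 10% at s = 0.5.

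**5. What bounds s?** LTE participants may enter the OLE on loss of response or after Week 52. Under the 36-month (156-week) limit in Protocol 4.1.4, someone who completes the LTE has 156 - 52 = 104 OLE weeks left, so the OLE Week 115 and 127 visits are out of reach. SAP 4.1.4.3 instead allows 143 OLE weeks, 13 + 39 + 143 = 195 in total. These passages must be reconciled, since they determine who can contribute at late visits.

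**6. Table 7 against its text.** Footnote a and the paragraph below the table limit the MMRM to Induction and to pooled Induction and LTE visits, with named weeks ending at 52 and no imputation. Footnote b says that summary statistics carry no between-arm comparisons. The comparison rows that mention OLE visits therefore have no model behind them.

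**The case against.** A reader might infer that every Week 13 responder counts as an OLE failure. The documents do not support that. Responders may enter the OLE on loss of response or after LTE Week 52 (SAP 4.1.3, 4.1.4.3), and under Protocol v.1 could enter regardless of response (SAP 4.1.4.1). Protocol Table 3 limits the Investigator's OLE Week 13 response assessment to Induction non-responders, but eDiary data are collected from all OLE participants.

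Non-responder imputation at OLE visits is also an inference. SAP 16.1.2 states it for the Week 13 primary outcome, the primary-analysis column of SAP Table 12 does not name exploratory endpoints, and SAP 9.8 defines a visit proportion over participants at that visit. With that denominator the example gives 50% vs 50%. This removes the counting artefact but not the problem: the test would compare groups selected on outcome, all on 60 mg.

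The protocol is not uniform either. Its section 9.4.1.3 has categorical exploratory endpoints analyzed like the primary, and section 3.2 defers OLE detail to the SAP. But 9.4.2 is the provision specific to the LTE and OLE.

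Finally, the SAP says that it covers the Induction period (SAP 2), that LTE and OLE data will appear in summaries and listings (SAP 5.2), and that any OLE testing is uncontrolled (SAP 16). This limits the consequence. It does not withdraw the CMH rule.

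**Conclusion.** The point holds as a defect in an exploratory analysis. On its text, SAP 16.4 calls for an as-randomized CMH test against placebo in the FAS at visits where all participants take 60 mg and entry depended on Week 13 response. The result would not be interpretable as a drug effect, and the departure from Protocol 9.4.2 is undeclared.

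Bias against the better Induction arm is possible, not built in. It needs FAS members without an OLE visit to be scored as non-responders, and LTE participants to reach the visit less often than Week 13 non-responders do. Under the assumed rates it runs from -12.5 points to 0. A reader might go further and conclude that an effective dose must look harmful in the OLE. That does not follow, because the gap closes when uptake is equal by both routes.

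Nor does Table 7 establish modelled between-arm comparisons at OLE visits; it shows a conflict between table and text. The primary and key secondary analyses and their Type I error control are unaffected.

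**What to change.** Take symptomatic response at OLE visits out of the CMH/FAS rule in SAP 16.4. Summarize it among participants who entered the OLE, as a subset of the FAS-ET, by original arm and route of entry (Week 13 non-response, loss of response in the LTE, LTE completion, Protocol v.1 entry). Give n, % and 95% CI, state the denominator at each visit, and make no between-arm test.

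In Table 7, remove the OLE visits from the FCP, CRP and PMS comparison rows so that the table agrees with the MMRM text and Protocol 9.4.2. In the same edit, assign the sixteenth endpoint to a rule and reconcile the maximum OLE duration between the protocol and SAP 4.1.4.3.

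The cost is SAP wording and table shells, with less analysis rather than more. OLE efficacy data are held for the end-of-study analysis (SAP 5.1, 5.2), so the change can be made before they are analyzed.

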4.1.4.1 Completion of Induction Week 13 - Protocol Version 1.0

Participants consented under Protocol v.1 and not re-consented to Protocol v.3 or later before the Induction Treatment Period Week 13 visit may have participated in OLE regardless of clinical response at Induction Treatment Period Week 13. These participants may have

reconsented to Protocol v.3 or later during OLE, and their scheduled OLE visits followed the OLE Schedule of Activities (SoA) specified by the newer Protocol version. Otherwise, the scheduled OLE visits followed the 39-week SoA specified by Protocol v.1.

Participants consented under Protocol v.1 who did not have clinical response at Induction Treatment Period Week 13 must have been assessed at OLE Week 13 for symptomatic response. Such participants who failed to achieve symptomatic response by OLE Week 13 (defined as decrease from baseline $\geq 30\%$ in composite RB and SF score) were discontinued from the study treatment and asked to complete the Early Termination (ET) and 1- and 2-Week Follow-up visits. However, participants who demonstrated symptomatic response at OLE Week 13 continued treatment with VTX002 60 mg in the OLE Treatment Period for up to an additional 26 weeks (a maximum OLE treatment duration of 39 weeks, and a maximum study treatment duration of 52 weeks).

4.1.4.2 Lack of Clinical Response at Induction Week 13 – Protocol Version 3.0 and Later

Participants who complete the Induction Week 13 visit, and do not meet the criteria for clinical response at Induction Week 13, will have the option to participate in the OLE for up to an additional 143 weeks of treatment (which includes a 7-day titration period followed by treatment with VTX002 60 mg for up to 142 weeks).

As non-responders, these participants will be assessed again for symptomatic response at OLE Week 13. At OLE Week 13, participants who fail to achieve symptomatic response will be discontinued from the study treatment and asked to complete the ET and 1- and 2-Week Follow-up visits. However, participants who respond to treatment by OLE Week 13 will continue treatment with VTX002 60 mg in the OLE Treatment Period for up to an additional 130 weeks (a maximum OLE treatment duration of 143 weeks, and a maximum study treatment duration of 156 weeks).

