4.3.3 Open-Label Extension Treatment

Participants entering the OLE Treatment Period will undergo a 7-day dose titration (OLE Days 1 to 8) to receive open-label VTX002 60 mg following the same titration schedule for the VTX002 60 mg as shown in Table 2. Although dose titration would not be needed for participants who received VTX002 60 mg during the Induction Period/LTE Period, all participants entering the OLE Treatment Period will go through a full dose titration regimen to maintain the blind of the Induction Period/LTE treatment assignments.

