24. APPENDIX III. VISIT LABEL MAPPING

EDC underwent significant changes between Protocol versions 1.0/2.0 and ≥ 3.0 , and especially for the OLE study period. The following visit mapping is intended to ensure that ADaM datasets utilize a consistent set of visit labeling conventions for tabulation, listing, and graphical purposes.

Table 10. Visit Label Mapping

Period	FolderName (Visit)		FolderName Mapped	PK Endpoints per Protocol	PK Sampling		
					Predose	2, 4, and 6 hours postdose (1, 2, 4 hrs postdose for V1)	24 hours postdose
Induction	Screening		Screening				
	Visit 2 Week 0		Visit 2 Week 0	Week 0	X	X	
	Visit 3 Week 1		Visit 3 Week 1	Week 1	X		
	Visit 4 Week 4		Visit 4 Week 4	Week 4	X		
	Visit 5 Week 8		Visit 5 Week 8	Week 8	X		
	Visit 6 Week 10		Visit 6 Week 10				
	Visit 7 Week 13		Visit 7 Week 13	Week 13	X - PV >2		
Long Term Extension (LTE)	LTE Visit 8 Week 13		LTE Visit 8 Week 13				
	LTE Visit 9 Week 18		LTE Visit 9 Week 18	Week 18	X		
	LTE Visit 10 Week 26		LTE Visit 10 Week 26	Week 26	X		
	LTE Visit 11 Week 36		LTE Visit 11 Week 36	Week 36	X		
	LTE Visit 12 Week 52		LTE Visit 12 Week 52	Week 52	X		
Open Label Extension (OLE)		OLE Week					
Protocol > V2	OLE Visit 1 Week 0	0	OLE Visit 1 Week 0		X	X	X
Protocol V1	Visit 8 Week 13	0	OLE Visit 1 Week 0		X		
	OLE Visit 2 Week 1	1	OLE Visit 2 Week 1		X	X	X
Protocol V1	Visit 9 Week 14	1	OLE Visit 2 Week 1				
	OLE Visit 3 Week 4	4	OLE Visit 3 Week 4		X	X	X
Protocol V1	Visit 10 Week 18	5	OLE Visit 3X Week 5				
	OLE Visit 4 Week 8	8	OLE Visit 4 Week 8		X		

Period	FolderName (Visit)		FolderName Mapped	PK Endpoints per Protocol	PK Sampling		
					Pre-dose	2, 4, and 6 hours postdose (1, 2, 4 hrs postdose for V1)	24 hours postdose
	OLE Visit 5 Week 13	13	OLE Visit 5 Week 13		X		
Protocol V1	Visit 11 Week 26	13	OLE Visit 5 Week 13				
	OLE Visit 6 Week 18	18	OLE Visit 6 Week 18		X		
Protocol V1	Visit 12 Week 36	23	OLE Visit 6X Week 23				
	OLE Visit 7 Week 26	26	OLE Visit 7 Week 26		X		
	OLE Visit 8 Week 36	36	OLE Visit 8 Week 36		X		
	OLE Visit 9 Week 39	39	OLE Visit 9 Week 39		X		
	Visit 13 Week 52 / End of Treatment	39	OLE Visit 9 Week 39				
	OLE Visit 10 Week 51	51	OLE Visit 10 Week 51				
	OLE Visit 11 Week 63	63	OLE Visit 11 Week 63				
	OLE Visit 12 Week 75	75	OLE Visit 12 Week 75				
	OLE Visit 13 Week 91	91	OLE Visit 13 Week 91		X		
	OLE Visit 14 Week 103	103	OLE Visit 14 Week 103				
	OLE Visit 15 Week 115	115	OLE Visit 15 Week 115				

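### SAP 16.4 tests the Week 18–52 responder endpoints in the FAS as randomized, with no rule for participants whom Protocol v1 let go straight from Week 13 to open-label 60 mg

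*SAP*

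**What the plan says.** **Endpoints and analysis.** SAP 16.4 lists 24 exploratory endpoints. Items 5 to 14 are remission and response endpoints at Weeks 18 to 52, for example "Proportion of participants with symptomatic remission at Weeks 18, 26, 36, and 52". The rule is "The first fifteen exploratory endpoints will be handled as responder analyses and analyzed similarly to the primary endpoint", by CMH test with as-randomized strata. The set is named: "The FAS set will be used for this purpose and treatment group comparisons" are as randomized, each dose against placebo. In the FAS (SAP 8), "participants are counted in the treatment group to which they were randomized, regardless of the treatment received during the study". SAP 16.5 repeats the FAS and the CMH test for four Week 18–52 rows of Table 8.

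**Path under Protocol v1.** SAP 4.1.4.1 says that participants not re-consented to v3 or later before Week 13 "may have participated in OLE regardless of clinical response at Induction Treatment Period Week 13". SAP 4.3.3 has everyone entering the OLE titrate "to receive open-label VTX002 60 mg following the same titration schedule" as the 60 mg arm. Under v3 and later (SAP 4.1.3), Week 13 responders instead stay on their blinded assigned treatment in the long-term extension (LTE) for up to 39 weeks.

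**Visit labels.** Table 10 in SAP Appendix III maps the v1 Week 18, 26 and 36 visits to OLE Weeks 5, 13 and 23. It maps "Visit 13 Week 52 / End of Treatment" to OLE Week 39.

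**Missing outcomes.** For the primary endpoint, SAP 16.1.2 gives "Primary method: single imputation as non-responder".

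**The concern.** A v1 participant in remission at Week 13 could be moved off blinded treatment by design, not because treatment failed. That participant is in the FAS but has no LTE visit at Weeks 18 to 52. SAP 16.4 gives no instruction for this case. Entering the OLE is not among the intercurrent events in SAP 3.5 or Section 16, and no text excludes or censors these participants.

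Two outcomes are possible:

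- The participant is scored as a failure at Weeks 18–52, which lowers the durability rates in every arm for an administrative reason.
- The OLE Week 39 result stands in for Week 52, so a placebo or 30 mg participant contributes a result obtained after 39 weeks of open-label 60 mg.

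Either way, the Week 52 comparison no longer contrasts the randomized treatments, and the choice is left to programming.

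**Working it through.** **1. The plan's own figure.** The only sample-size calculation is for Week 13 clinical remission (SAP 6 and Appendix VII): 28% vs 8%, two-sided 5%, 80% power, chi-squared test. With mean rate 0.18:

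n = [1.96·√(2·0.18·0.82) + 0.842·√(0.08·0.92 + 0.28·0.72)]² / 0.20² = 56.7, so 57 per arm with power 0.802.

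This agrees with the SAP, and 57 × 1.10 = 62.7 gives the stated 63. No rate or power is given for Weeks 18–52.

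**2. Visit arithmetic.** The OLE starts at Week 13 for these participants. Thus 18 − 13 = 5, 26 − 13 = 13, 36 − 13 = 23 and 52 − 13 = 39, which matches Table 10. By label these are OLE visits. By total time on treatment, OLE Week 39 is Week 52 (13 + 39), and SAP 4.1.4.1 itself gives 52 weeks as the v1 maximum. Several endpoints in 16.4 are worded as time on treatment, so the label alone does not settle the matter.

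**3. Illustration of size.** Assumptions, none from the documents for Week 52: true rates of 28% and 8% borrowed from Week 13, 63 per arm, the same share v of each arm moved to the OLE under v1, and 28% remission on open-label 60 mg.

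- Scored as failures: each rate × (1 − v), so the difference is 20 × (1 − v) points.
- OLE results credited to the randomized arm: 60 mg stays at 28%, placebo becomes 8(1 − v) + 28v %, so the difference is again 20 × (1 − v) points.

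| v | participants per arm (63v) | failures: rates | credited: rates | difference (points) | power, failures | power, credited |
|---|---|---|---|---|---|---|
| 0 | 0 | 28.0 vs 8.0 | 28.0 vs 8.0 | 20 | 0.84 | 0.84 |
| 5% | 3.2 | 26.6 vs 7.6 | 28.0 vs 9.0 | 19 | 0.82 | 0.79 |
| 10% | 6.3 | 25.2 vs 7.2 | 28.0 vs 10.0 | 18 | 0.79 | 0.74 |
| 20% | 12.6 | 22.4 vs 6.4 | 28.0 vs 12.0 | 16 | 0.73 | 0.61 |

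**4. Unequal shares.** Under failure scoring with 0% of the 60 mg arm and 10% of placebo affected, the difference is 28.0 − 7.2 = 20.8 points. With 10% and 0%, it is 25.2 − 8.0 = 17.2. The direction is therefore not fixed. The plan gives no assumed rate for 30 mg, so that comparison cannot be illustrated in the same way.

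**The case against.** The strongest reply is that failure scoring is not actually prescribed here, and this stands. A reader might infer that the SAP counts these participants as failures, but the text does not go that far:

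- SAP 16.1.2 concerns missing Week 13 primary outcomes.
- The non-responder column of Table 12 covers primary, key secondary and other secondary endpoints, not exploratory ones.
- SAP 3.5 extends only the population, the intercurrent-event strategy and the summary measure to exploratory endpoints, and only in general.
- SAP 16.5 says that no imputation is performed.

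Failure scoring is one reading of being analysed like the primary endpoint, not a stated rule.

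Other points on that side:

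- **Table 7 conflicts.** It places symptomatic response and remission at Weeks 18–52 in FAS-ET with summary statistics and no formal comparison. These are the only responder endpoints on the list at Weeks 18, 26 and 36, so there the defect is first a contradiction with the FAS rule in 16.4. The clinical, endoscopic and histologic Week 52 responder endpoints are not in Table 7.
- **Separate analysis by period.** SAP 16.4 allows LTE and OLE analyses to use different participant sets, and FAS-ET generally groups by intended dose. But 16.4 names no alternative set for the responder endpoints, and it does name the FAS.
- **Crediting 60 mg results to other arms.** Table 10 keeps OLE Week 39 apart from LTE Week 52, which weakens this reading. The time-on-treatment wording keeps it open.
- **Consequence.** The SAP's stated scope is the Induction period. LTE and OLE data stay out of the Induction Period Analysis (SAP 5.1), and their tests are uncontrolled (SAP 16). Protocol 9.4.2 foresees summaries only. This limits the consequence but does not supply the missing rule.

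**Conclusion.** The point holds as a gap and an internal conflict. SAP 16.4 fixes a set and a test for the Week 18–52 responder endpoints that cannot be applied sensibly to participants whom v1 let move straight to open-label 60 mg, and it does not say which of two unsatisfactory treatments applies.

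The size is unknown. The documents give neither the number of such participants nor their split by arm. The four randomized participants with a baseline MMS of 4 do not provide a count, since Section 16 excludes them from all efficacy analyses except one sensitivity analysis. The shrinkage from 20 to 19, 18 or 16 points rests entirely on the assumptions in the working.

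A reader might also infer that the trial's main conclusions are at risk. They are not: the Week 13 primary and key secondary tests are unaffected. What is at stake is the reading of exploratory durability results with nominal p-values.

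**What to change.** Amend SAP 16.4 and 16.5 as follows:

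1. State that OLE visits, including the mapped OLE Week 39, never count as Weeks 18–52 of randomized treatment.
2. Restrict the as-randomized Week 18–52 responder analyses to participants whose scheduled Week 13 date fell after Protocol v3 or later took effect at their site. Apply this to everyone, including those who dropped out before Week 13. Excluding only those who reached Week 13 under v1 would keep v1 dropouts in the set, as failures if missing is so scored, while removing v1 completers, and completion can depend on arm and outcome. The scheduled date cannot.
3. State that participants under v3 or later who move to the OLE for non-response or loss of response are non-responders from that point.
4. Reconcile the FAS/CMH rule with Table 7 (FAS-ET, descriptive) and with Protocol 9.4.2.

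Summarise the excluded v1 participants in the OLE tables. Say also how to handle anyone whose date falls after the switch but who was never re-consented. The first-fifteen and last-eight rules cover 23 of the 24 listed endpoints, so the same edit should assign an analysis to the Week 52 Geboes decrease endpoint.

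The cost is SAP wording, the site dates on which v3 or later took effect, and a smaller denominator for exploratory endpoints. The rule is best settled before the interim database lock, because the Sponsor is unblinded to LTE assignments after it.
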